6. STATISTICAL ANALYSES

6.1 Baseline data and operative data

Baseline data (i.e. patient demography and past history) will be described by treatment group for patients in the analysis population. **Table T4** will be used as a template for this.

Continuous variables will be summarised using the mean and standard deviation (SD) (or median and inter quartile range (IQR) if the distribution is skewed), and categorical data will be summarised as a number (n/N) and percentage.

Any imbalances in the characteristics of the patients at the start of the study will be described but statistical tests for baseline imbalance will not be carried out.

Operative details will be described by treatment group for patients in the analysis population. **Table T5** will be used as a template for this.

6.2 Primary and secondary outcome data

Primary and secondary outcome data will be described by treatment group for patients in the analysis population. The choice of summary statistics will be as for the baseline data. Treatment effects will be reported graphically with 95% confidence intervals (CIs), and with numerical details alongside (cf. Forest plot). **Figures F4 to F7** will be used as templates for this.

6.2.1 Adjustment in models

The intention is to adjust all models for centre and the factors included in the cohort minimisation: operating surgeon, both as random effects. If there is a change in surgeon after randomisation, models will adjust for the surgeon who performed the intervention and not the surgeon originally allocated to perform the procedure.

If the frequency of the outcome is insufficient to allow estimation of regression coefficients for all these variables (e.g. rare binary outcomes), the variables with coefficients that cannot be estimated will be omitted.

For continuous outcomes that are measured preoperatively as well as postoperatively, preoperative and postoperative values will be modelled jointly in preference to the preoperative value being modelled as a covariate. Joint modelling will avoid the necessity to either exclude cases with missing baseline measures or to impute missing baseline values.

6.2.2 Analysis models

All outcomes listed in the study protocol will be presented as per the template tables **Table T11 to T18**. General methods of presentation and assessing treatment effects are outlined below. For all treatment comparisons, the open lobectomy group will be the reference group. Details specific to each outcome are described as appropriate.

Each outcome will be considered under a certain data type, as outlined in the table below:

Date type	Outcomes
Binary	Proportion of patients receiving adjuvant treatment Proportion of patients who undergo complete resection during the procedure Proportion of patients who experience prolonged incision pain Any in-hospital adverse event Any in-hospital serious adverse event
Categorical	Proportion upstaged to pN1 disease after the procedure Proportion upstaged to pN2 disease after the procedure
Time to event	Time from surgery to hospital discharge Time to uptake of adjuvant treatment Overall survival Disease-free survival
Longitudinal	Physical function (primary) Pain scores in the first two days post-surgery HRQoL (QLQ-C30, QLQ-LC13, EQ5D)

Each type of data will be summarised and compared between the groups according to the following:

- **Binary outcomes** will be presented as numbers and percentages of patients in each treatment group. Outcomes will be compared between treatment groups using generalised linear models, with treatment comparison estimates presented as adjusted risk ratios (RR) and risk differences (RD) with 95% confidence intervals (95% CI). Formal statistical comparisons of treatment effects will only be performed if more than ten patients in total experience the outcome (with at least one event in each treatment group).
- **Categorical outcomes** will be presented as numbers and percentages of patients in each treatment group in each category. Outcomes will be compared between treatment groups using multinomial logistic regression, with treatment comparison estimates presented as adjusted RR and 95% CI.
- **Time to event outcomes** will be summarised by the median and IQR or mean and SD in each treatment group, estimated from survival modelling. Outcomes will be compared using Cox’s proportional hazards, parametric models, or interval censoring methods for analysing discrete time data, as appropriate. The choice of model used will depend on the outcome event and the distribution of the data. Treatment comparisons will be presented as hazard ratios (HRs) and 95% CI if a proportional hazards model is used, time ratios (TRs) and 95% CI if an accelerated failure time model is used, or OR and 95% CI if a discrete time proportional odds model is used. Times will be censored using censoring variables defined below:

Outcome	Censor variable
Time from surgery to hospital discharge	Date of death, if patient died before hospital discharge
Time to uptake of adjuvant treatment	Last visit date, if patient did not receive any adjuvant treatment
Overall survival	Last visit date, if patient was alive at the end of the study follow-up
Disease free survival	Last visit date, if patient was disease free at the end of the study follow-up

- **Continuous longitudinal outcomes** will be summarised as means and SDs (or medians and IQRs if distributions are skewed) at each time point. Outcomes will be compared using linear mixed effects methodology with the treatment group and study design variables fitted as per section 5.2.1, and patient terms fitted as random effects. Separate parameter estimates will be incorporated into models for 1) the mean baseline response across both treatment groups and 2) at each post-intervention time point for each treatment (i.e. saturated model with time fitted as a categorical variable). If the time x treatment interaction (post-intervention) is not statistically significant at the 10% level an overall treatment effect will be reported. If the interaction is statistically significant the changes in treatment effect with time will be described. Deaths will be accounted for by modelling HRQoL and survival jointly. When modelling EQ5D, patients who have died will be assigned a score of 0 for all future time points. Different variance/covariance structures will be explored, and the structure that provides the best fit in terms of information criteria such as AIC, BIC and likelihood ratio tests will be used. Treatment comparisons will be presented as adjusted differences in means with 95% CI.

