5.2 Secondary outcomes

1. Time from surgery to hospital discharge

Both time from surgery until first fit for discharge, and time from surgery until hospital discharge will be described. Time from surgery until hospital discharge will be compared between groups.

New variable	Rules
Time from surgery to hospital discharge	= (Discharge date – operation date)
Fit for discharge	YES: if satisfactory mobility = YES AND pain under control with oral analgesia = YES AND satisfactory Hb & electrolytes = YES AND satisfactory chest X-ray = YES (or satisfactory on a previous day and not necessary to repeat) AND free from complications requiring treatment = YES NO: if satisfactory mobility = NO OR pain under control with oral analgesia = NO OR satisfactory Hb & electrolytes = NO OR satisfactory chest X-ray = NO (or not done and not previously satisfactory) OR free from complications requiring treatment = NO MISSING: otherwise
Time from surgery to fit for discharge	= (First day fit for discharge – operation date)

2. Pain scores in the first two days post-surgery

Pain scores are collected at baseline (prior to surgery), day one post-surgery and day two post-surgery. Pain scores are collected directly on CRFs using the visual analogue scale (VAS) and so no derivation is required.

3. Adverse health events to 1 year

All adverse events occurring at any time during the 12 month follow-up period will be reported.

New variable	Rules
Maximum intensity of SAE (CTCAE)	Maximum of CTCAE variable on initial SAE form and all follow-up SAE forms

4. Proportion and time to uptake of adjuvant treatment

The proportion of patients receiving adjuvant treatment at any time during the 12 month follow-up period will be described. The time to uptake of adjuvant treatment will be calculated as follows:

New variable	Rules
Uptake of adjuvant treatment	YES: if at any study visit, chemotherapy or radiotherapy started = YES NO: if at all attended study visits, chemotherapy and radiotherapy started = NO MISSING: otherwise
Time to uptake of adjuvant therapy	= (Earliest chemotherapy/radiotherapy start date - randomisation date)

5. Proportion of patients upstaged to pN2 disease after the procedure

The proportion of patients upstaged to pathological N2 disease following surgery will be derived as follows:

New variable	Rules

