6.2.6 Sensitivity analyses

A pre-specified sensitivity analysis excluding participants with benign disease will be performed for the primary outcome (see Table T21).

Sensitivity analyses of overall survival and disease-free survival will be performed, adjusting for patient's disease stage based on pathological findings (see Figure F11).

Note: these analyses of survival were not pre-specified in the protocol but added upon recommendation from the Data Monitoring and Safety Committee (DMSC).

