Analyses are adjusted for operating surgeon and centre

Table T24 Exploratory analysis comparing length of stay by number of port sites

Outcome	Median	IQR	Effect size	95% confidence interval	p-value
Length of stay					
Single port VATS vs multi port VATS			MD=X.XX	(X.XX, X.XX)	
Single port VATS vs open			MD=X.XX	(X.XX, X.XX)	X.XX
Multi port VATS vs open			MD=X.XX	(X.XX, X.XX)	

Analyses are adjusted for operating surgeon and centre

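### Time to discharge is censored at in-hospital death, so the hazard ratio is an unlabelled cause-specific one and the per-arm stay summaries assume that patients who died would later have gone home

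*SAP*

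**What the plan says.** Section 5.2, item 1, defines the outcome as discharge date minus operation date and states: "Time from surgery until hospital discharge will be compared between groups".

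Section 6.2.2 classes it as a time-to-event outcome. The censoring table gives "Date of death, if patient died before hospital discharge". Such outcomes "will be summarised by the median and IQR or mean and SD in each treatment group, estimated from survival modelling", and the comparison may use Cox's model, "parametric models, or interval censoring methods for analysing discrete time data, as appropriate". The effect measure is an HR, a time ratio or an odds ratio, depending on the model. Table T12 shows an HR for duration of stay.

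No cumulative incidence, subdistribution or worst-outcome method is named for this outcome. Section 6.2.6 has sensitivity analyses for two other time-to-event outcomes ("Sensitivity analyses of overall survival and disease-free survival will be performed, adjusting for patient's disease stage based on pathological findings") but none for stay.

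Section 6.2.2 does deal with death explicitly for other outcomes. For quality of life, "Deaths will be accounted for by modelling HRQoL and survival jointly". For EQ5D, "patients who have died will be assigned a score of 0 for all future time points".

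**The concern.** Ordinary censoring means that the event is still to come but was not observed. A patient who dies in hospital will never be discharged, so the censoring rule sets aside a known outcome as if it were unknown. Two things follow.

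- **The HR.** It describes how fast patients go home while they are alive in hospital. It cannot show that fewer patients in one arm went home at all. Nothing in section 6.2.2 or Table T12 tells the reader this.
- **The per-arm summaries.** A survival curve with deaths censored rises to 100% discharged. Its quantiles and mean describe a ward in which the dead would have left later. Calling the HR cause-specific does not repair these summaries.

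Hospital stay is the first efficacy item in objective (b) of section 2.2, so its meaning should be fixed before the data are seen. Whether deaths are balanced is known only afterwards.

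**Working it through.** The SAP states no figure on this point that could be reproduced. It supplies 498 patients at 1:1 (section 3 and section 3.2), hence 498 / 2 = 249 per arm, and the censoring rule. Mortality and stay below are assumptions.

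**Two rules compared.** Rule A is the SAP's: a Cox model with deaths censored on the date of death. Rule B keeps deaths in the risk set beyond the longest stay, as never discharged. With no other censoring, rule B gives the Fine-Gray subdistribution HR.

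**Setting 1.** The discharge hazard is constant and equal in both arms, λ = ln 2 / 5.5 per day. The death hazard is μ = λp/(1 − p), so a proportion p dies in hospital. Limiting HRs come from 400,000 per arm; the share of trials with p < 0.05 comes from 2,000 trials of 249 per arm.

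| Mortality | HR, rule A | HR, rule B | p < 0.05, A | p < 0.05, B |
|---|---|---|---|---|
| 1% v 1% | 1.00 | 1.00 | 6% | 6% |
| 2% v 1% | 1.00 | 0.97 | 5% | 6% |
| 3% v 1% | 1.00 | 0.94 | 4% | 10% |
| 5% v 1% | 1.00 | 0.89 | 5% | 24% |
| 5% v 0% | 1.00 | 0.86 | 5% | 39% |

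The HR is for the arm with more deaths; below 1 means slower discharge. The standard error of the log HR is about 0.09.

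**Setting 2.** Log-normal stay, log-SD 0.6, rounded up to whole days, median 5 days in the open arm, death at a uniform point of the stay, 249 per arm.

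| Median, open / VATS | Mortality, open v VATS | HR, A | HR, B | B / A |
|---|---|---|---|---|
| 5 / 5 | 1% v 2% | 0.998 | 0.959 | 0.961 |
| 5 / 5 | 1% v 3% | 0.984 | 0.918 | 0.933 |
| 5 / 4.5 | 1% v 1% | 1.166 | 1.147 | 0.984 |
| 5 / 4.5 | 1% v 2% | 1.171 | 1.106 | 0.944 |
| 5 / 4.5 | 1% v 3% | 1.154 | 1.053 | 0.912 |

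With unequal mortality of 1% versus 2 to 3%, the two rules differ by about 4 to 7% when stays are equal and 6 to 9% when VATS truly shortens stay. Overall this is roughly 4 to 8%.

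**Per-arm summaries.** In setting 1 the quantiles have closed forms. Under rule A the q-quantile is −ln(1 − q)/λ. From the cumulative incidence of discharge alive, (1 − p)[1 − exp(−λt/(1 − p))], it is −((1 − p)/λ) ln(1 − q/(1 − p)). With λ = 0.126 and p = 0.03:

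- Median: 5.50 days against 5.58 days.
- 75th percentile: 11.0 against 11.4 days.
- 90th percentile: 18.3 against 20.2 days.

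In a log-normal scenario with dying patients as a separate group, the median is 6 days under either rule. At 5% mortality the 90th percentile is 13 to 14 days with deaths censored and 15 days with deaths as never discharged.

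**Does rule B carry over to a parametric model?** With log-normal stay, equal medians and 1% versus 3% mortality, an accelerated failure time model gives a time ratio of 1.003 under the SAP rule. Deaths censored one day past the longest stay give 1.035, at day 60 they give 1.048, and at day 365 they give 1.084. The answer depends on an arbitrary date, so the device suits a Cox-type model only.

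**Table T24.** Sections 6.2.2 and 6.2.7 and the two tables do not agree. Section 6.2.2 allows an HR, time ratio or odds ratio for this outcome and Table T12 uses an HR. Table T24 compares the same outcome by port sites with median and IQR columns and an effect labelled MD.

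**The case against.** The cause-specific HR is a legitimate estimand, and arguably the cleaner one for speed of recovery, because it does not mix mortality with discharge. Deaths are not hidden from the trial: overall survival is compared, in-hospital serious adverse events appear in Table T12, and section 6.3 describes whether patients were alive or died after a serious event. One versus two per cent of 249 is about 2.5 versus 5 deaths. With equal stays, the log-HR gaps in setting 1 are 0.035 and 0.066, or 0.4 and 0.7 of a standard error. All of this stands and limits the size of the point. It does not rescue the per-arm summaries, and Table T12 has no row for in-hospital death.

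Three stronger readings might be inferred but are not supported:

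- **That the HR is biased in favour of the arm with more deaths.** With equal stays, rule A gives 1.00 in setting 1 and 0.998 and 0.984 in setting 2. It does not favour that arm; it is simply silent about the deaths. The gap exists only relative to a different estimand.
- **That intention to treat forbids the rule.** Section 3.5 defines who is analysed, and censored patients remain in the analysis. The clock starts at surgery under either rule.
- **That Table T24 counts an early death as a short stay.** The SAP does not say how T24 handles a death, and section 6.2.2 allows means estimated from survival modelling. Only the mismatch in effect measure is established.

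**Conclusion.** The point holds in limited form. The SAP treats a competing event as ordinary censoring for time to discharge. The resulting HR is valid as a cause-specific rate ratio but is unlabelled and does not reflect excess in-hospital deaths. The per-arm summaries rest on the wrong premise that patients who died would later have been discharged.

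Under assumed mortality of 1% versus 2 to 3%, the HR differs by about 4 to 8% between the two approaches. The median stay barely changes, and the effect is seen mainly in the upper quantiles. With 1% mortality in each arm the difference is at most about 2%. It becomes material only with an imbalance of around 4 to 5 percentage points. All of these sizes rest on assumed mortality and stay distributions, because the SAP gives neither. The primary outcome is not affected.

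**What to change.** In the time-to-event part of section 6.2.2:

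1. Treat in-hospital death as a competing event for time from surgery to discharge, and replace the censoring entry accordingly.
2. Take each arm's quantiles from the cumulative incidence of discharge alive.
3. Name a Cox-type subdistribution (Fine-Gray) HR, with deaths kept in the risk set beyond the longest stay. State that this device is not used with accelerated failure time or other parametric models.
4. Report the present HR alongside, labelled cause-specific, and add in-hospital deaths by arm to Table T12.

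Separately, reconcile the MD in Table T24 with the HR in Table T12, or say how the MD is estimated and how deaths enter it.

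The cost is a changed table entry, a few lines on the model and small template edits. No new data are needed. Two costs are real. Naming the model narrows the open choice in section 6.2.2 for this outcome. The subdistribution HR also mixes mortality with speed of discharge, which is why the cause-specific HR should stay beside it.

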2.2 Study objectives

The VIOLET study aims to compare the effectiveness, cost-effectiveness and acceptability of VATS lobectomy versus open surgery for treatment of lung cancer.

Specific objectives are to estimate:

- (a) The difference between groups in self-reported physical function at five weeks
- (b) The difference between groups with respect to a range of secondary outcomes including assessment of efficacy (hospital stay, pain, proportion and time to uptake of chemotherapy), measures of safety (adverse health events), oncological outcomes (proportion of patients upstaged to pN2 disease and disease-free survival) and overall survival.
- (c) The cost effectiveness of VATS and open surgery.

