2.3 Primary outcome

The primary outcome is self-reported physical function, assessed using the QLQ-C30 questionnaire, at 5 weeks post-randomisation.

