3. STUDY POPULATION

The study population is all patients aged ≥ 16 years of age who have been referred by the multi-disciplinary team (MDT) for lung resection for known or suspected lung cancer. Eligibility criteria are as inclusive as possible to promote the applicability of the evidence obtained during the trial. For specific inclusion/exclusion criteria see **Figure F1**.

Recruitment over time against targets will be presented overall (**Figure F2**).

The planned sample size for the VIOLET study is 498 patients. This sample size would be sufficient to detect a difference of 0.25 standard deviations in physical function between the VATS and open groups with 90% power and 5% significance (2-tailed). The total sample size will allow for a 20% dropout at one year.

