6.2.9 Multiple testing

For quality of life outcomes derived from the QLQ-C30 and QLQ-LC13 questionnaires, multiple testing will be accounted for by applying the false discovery rate method proposed by Benjamini Y and Hochberg Y⁽⁵⁾. This method will be applied within each instrument (e.g. for QLQ-C30 functional scale scores, QLQ-C30 symptom scale scores and QLQ-LC13 scores). No formal adjustment will be made for multiple testing for other outcomes. However as previously described formal statistical comparisons will not be made for outcomes with low event rates and only pre-specified subgroup analyses will be performed. Consideration will be taken in interpretation of results to reflect the number of statistical tests performed and the consistency, magnitude and direction of treatment estimates for different outcomes.

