Blinding index (VATS: open) = X.XX (95% confidence interval [CI], X.XX to X.XX): X.XX (95% CI, X.XX to X.XX) (P=X.XX).

Table T8 Nurse blinding at discharge

Intervention	VATS	Nurse's answer, n (%)			Question not asked, n
		Open	Do not know	Total	
VATS					
Open					
Total					

Blinding index (VATS: open) = X.XX (95% confidence interval [CI], X.XX to X.XX): X.XX (95% CI, X.XX to X.XX) (P=X.XX).

Table T9 Nurse blinding at 5 weeks

Intervention	VATS	Nurse's answer, n (%)			Question not asked, n
		Open	Do not know	Total	
VATS					
Open					
Total					

Blinding index (VATS: open) = X.XX (95% confidence interval [CI], X.XX to X.XX): X.XX (95% CI, X.XX to X.XX) (P=X.XX).

Table T10 Nurse blinding at 12 months

Intervention	VATS	Nurse's answer, n (%)			Question not asked, n
		Open	Do not know	Total	
VATS					
Open					
Total					

Blinding index (VATS: open) = X.XX (95% confidence interval [CI], X.XX to X.XX): X.XX (95% CI, X.XX to X.XX) (P=X.XX).

Table T11 Primary outcome

Outcome		Randomised to open (n=XX)		Randomised to VATS (n=XX)		Effect (95% CI)	p-value
		Mean/Median	SD/IQR	Mean/Median	SD/IQR		
Physical functioning	Baseline						
	2 weeks						
	5 weeks					MD/GMR	
	3 months						
	6 months						
	12 months						
Test for treatment*time interaction							
Overall treatment effect estimate						MD/GMR	

Notes: higher scores indicate higher levels of functioning
Analyses are adjusted for operating surgeon and centre

Figure F4 Primary outcome

[figure not shown]

Table T12 In-hospital secondary outcomes

Outcome	Randomised to open (n=XX)	Randomised to VATS (n=XX)	Effect (95% CI)	p-value
Duration of hospital stay (days)			HR	
Upstaged from cN0 to pN1 disease after procedure			HR	
Upstaged from cN0 to pN2 disease after procedure			RR/RD	
Complete R(0) resection during procedure			RR/RD	
Any in-hospital adverse event			RR/RD	
Any in-hospital serious adverse event			RR/RD	

Values are presented as median (interquartile range), mean (standard deviation), or n (%). Analyses are adjusted for operating surgeon and centre

Table T13 Post-discharge secondary outcomes

Outcome	Randomised to open (n=XX)	Randomised to VATS (n=XX)	Effect (95% CI)	p-value
Received adjuvant treatment			RR/RD	
Time to uptake of adjuvant treatment (months)			HR	
Overall survival (months)			HR	
Disease-free survival (months)			HR	
Prolonged incision pain			RR/RD	

Values are presented as median (interquartile range) or n (%).
Analyses are adjusted for operating surgeon and centre

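### The SAP does not say which of Table T11's two estimates, the 5-week effect or the overall effect, is the primary test, and its 10% interaction rule points away from 5 weeks

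*SAP*

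**What the plan says.** The target is stated consistently. SAP section 2.2, objective (a), is to estimate "The difference between groups in self-reported physical function at five weeks". Section 2.3 says "The primary outcome is self-reported physical function, assessed using the QLQ-C30 questionnaire, at 5 weeks post-randomisation", and section 5.1 repeats the time point.

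The analysis rule is in section 6.2.2. Its table of data types puts physical function, marked there as the primary outcome, in the longitudinal class with the pain scores and the other quality-of-life scales. The model for that class is saturated, with time as a categorical variable and a separate mean for each treatment at each post-intervention visit. One reporting rule covers the whole class: "If the time x treatment interaction (post-intervention) is not statistically significant at the 10% level an overall treatment effect will be reported". When that test is significant, the plan promises a description of how the effect changes over time. No exception is made for the primary outcome.

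Table T11 in Appendix A is the template for the primary outcome. As it reads in the copy reviewed, it has an effect cell in the 5-week row, a row for the interaction test, and a row labelled "Overall treatment effect estimate". No note says which of the two estimates is the primary result. Section 6.2.3 applies the two-sided 5% criterion to hypothesis tests generally.

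**The concern.** The overall effect combines 2 weeks, 5 weeks, 3 months, 6 months and 12 months. It equals the 5-week effect only if the treatment difference is constant, and a non-significant interaction test does not establish that.

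The rule in section 6.2.2 therefore points the reader of a non-significant interaction to a quantity that objective (a) does not name, and T11 supplies a p-value for it beside the 5-week one. If the two disagree, the SAP gives no rule for which settles the superiority question. A recovery benefit that fades could be summarised by a diluted average. Equally, a trial with no difference at 5 weeks could be called positive on the strength of other visits. The choice would be made after seeing the data, so the selected estimate would not carry its nominal error rate as a test of the 5-week hypothesis.

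**Working it through.** **Inputs from the SAP.** 498 patients, 1:1, so 249 per arm; after the 20% one-year loss in section 3, 249 × 0.8 = 199 per arm. Five post-intervention visits, so the interaction has 4 degrees of freedom. Pre-test level 10%; final tests two-sided 5%.

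**Assumptions, because the SAP gives none.** Compound symmetry with correlation ρ between all visits including baseline, unit SD, a common baseline mean, and the effect patterns below.

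**Formulas.** With visit effects δ and their mean δ̄, the interaction statistic is noncentral chi-square on 4 df with λ = (n/2) Σ(δ − δ̄)² / (1 − ρ). The 10% critical value is 7.78. The variance of the 5-week estimate is (2/n)(1 − ρ²), and that of the five-visit mean is (2/n)[(1 + 4ρ)/5 − ρ²].

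**Case 1: fading benefit, 0.25, 0.25, 0.15, 0.10, 0.10 SD.** The mean is 0.17 and Σ(δ − δ̄)² = 0.0064 + 0.0064 + 0.0004 + 0.0049 + 0.0049 = 0.023.
- n = 199, ρ = 0.5: λ = 99.5 × 0.023 / 0.5 = 4.58; the interaction is missed in 51% of trials.
- n = 249, ρ = 0.7: λ = 124.5 × 0.023 / 0.3 = 9.55; missed in 21%.

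When it is missed, the rule calls for an overall effect whose target is 0.17 SD, which is (0.25 − 0.17)/0.25 = 32% below the 5-week effect.

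**Case 2: no effect at 5 weeks, 0.15 SD at the other four visits.** The mean is 0.12 and Σ(δ − δ̄)² = 4 × 0.0009 + 0.0144 = 0.018. Suppose the overall test is used when the interaction is not significant and the 5-week test when it is. The second half is a reading added to make the rule complete, because the SAP promises only a description there. By simulation, with at least 400,000 draws per setting and ρ from 0.4 to 0.7:
- Highest, n = 249, ρ = 0.4: the interaction is missed in 57.8%; the overall test rejects in 60.6% of those trials and the 5-week test in 6.2% of the rest. 0.578 × 0.606 + 0.422 × 0.062 = 0.38.
- Lowest, n = 249, ρ = 0.7: missed in 30.9%; the rejection rates are 73.0% and 4.2%. 0.309 × 0.730 + 0.691 × 0.042 = 0.255, about 26%.

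The fixed 5-week test rejects in 5% throughout.

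**Cases where little is at stake.**
- No effect at any visit: 0.90 × 0.05 + 0.10 × about 0.15 = about 6.0%, against 5.0%.
- Constant effect: the overall effect is chosen in 90% of trials but has the same target as the 5-week effect, so it is unbiased.
- Sharp early-only effect, 0.25, 0.25, 0, 0, 0: the interaction is usually detected, and the overall effect is chosen in only about 0% to 11% of trials (ρ 0.4 to 0.7).

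**The case against.** The strongest reply is that the 5-week effect will be reported anyway. The SAP declares it three times, the saturated model always yields it, and T11's 5-week effect cell appears unconditional. T11 shows an effect at no other visit, whereas T15 shows one at every visit. Sections 1.4 and 6.2.2 give the templates standing. Most of this holds. A reader might infer that the pre-test decides whether the 5-week effect appears at all; the SAP does not support that. Nor is the 5-week effect the other branch of the rule. But printing an estimate does not make it the primary test, and no sentence does so. Cell placement in the extracted tables is imperfect, and Figures F4 and F7 are not visible, so neither can settle the matter.

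A second reply is that the figures rest on chosen effect patterns and correlations. That is correct, and the harmless cases are given with the others.

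Two further inferences are tempting and should not be drawn.
- **Power.** Section 3 says the sample can "detect a difference of 0.25 standard deviations in physical function between the VATS and open groups with 90% power and 5% significance (2-tailed". An unadjusted two-sample formula gives 2 × (1.960 + 1.282)² / 0.25² = 336 per arm, far more than 249. But the planned model uses baseline, and 498 follows from a baseline correlation of about 0.64 with 20% loss or 0.51 with none. It also follows from a five-visit average with correlations of 0.6 between visits and 0.3 with baseline. The protocol, not at hand, may state such values. No error is shown, and 498 does not reveal which contrast was powered.
- **False discovery rate.** Section 6.2.9 opens with "For quality of life outcomes derived from the QLQ-C30 and QLQ-LC13 questionnaires, multiple testing will be accounted for", which could be read to include the primary outcome. However, T15, the table for the functional scales, omits physical functioning, and section 6.2.2 lists it apart from the other HRQoL scales. Exclusion looks intended.

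**Conclusion.** The point stands as an unresolved conflict within the SAP. Sections 2.2, 2.3 and 5.1 fix 5 weeks; section 6.2.2 applies to the primary outcome a data-dependent rule that never names 5 weeks; and Table T11 shows two estimates without ranking them. It should be fixed, because it concerns the trial's main conclusion. It does not show that the result will answer the wrong question.

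The consequence ranges from negligible (constant effect, or about 1 point of extra type I error under a global null) to material under the fading and zero-at-5-weeks patterns worked above. Those larger figures depend on compound symmetry, 199 to 249 per arm and the assumed effects and correlations. The second also depends on using the 5-week test when the interaction is significant.

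**What to change.** In section 6.2.2, and in a note to Table T11, state that the primary analysis is the VATS minus open mean difference in physical function at 5 weeks, estimated from the saturated model already specified and tested two-sided at 5%, whatever the interaction result. State that the overall effect, the interaction test and the other visits are secondary for this outcome. The existing rule can stay for the other longitudinal outcomes.

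Optionally, add a clause to section 6.2.9 confirming that the primary outcome lies outside the false-discovery-rate families, as T15 already implies. No restatement of power is asked for.

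The cost is a few sentences in an SAP amendment, with no new model, data or patients. One thing is given up: if the effect is truly constant, the average is the more precise estimate. For a constant 0.25 SD at ρ = 0.6 and 199 per arm, its test rejects in 99% of trials against 88% for the 5-week test. That information remains available as a secondary result.
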